Original	March 27, 2020	N/A
V2.0	April 13, 2020	Revised study title and added 3 months of longitudinal follow-up
V3.0	December 7, 2020	Revised duration of follow-up from 3 months to 12 months, removed questions on social distancing, and added questions on mental health conditions, healthcare encounters, and vaccines.
V4.0	March 9, 2021	Revised inclusion criteria to include vaccinated adults as well as participants from the UK; added questions about post-vaccination symptoms and health care encounters.

List of Abbreviations

COVID-19	coronavirus disease 2019
FDA	U.S. Food and Drug Administration
GDPR	General Data Protection Regulation
GPP	good pharmacoepidemiology practices
HIPAA	Health Insurance Portability and Accountability Act of 1996
ICF	informed consent form
ICH	International Council for Harmonisation of Technical Requirements for Pharmaceuticals for Human Use
IEC	independent ethics committee
IRB	institutional review board
ISPE	International Society for Pharmacoepidemiology
NSAID	nonsteroidal anti-inflammatory drugs

Study Synopsis

Full Study Title: Registry to study factors that may impact COVID-19 occurrence and severity

Background & Rationale: The 2019 coronavirus disease (COVID-19) has presented major challenges to countries around the world. Currently there is little information about (1) symptom presentation, severity, and duration especially for cases that do not require hospitalization, (2) understanding which prescription medications, if any, influence risk, including various hypertension and anti-diabetic medications, (3) whether vitamin and mineral supplements, alone or in combination with established medications offer any degree of protection, and (4) what medical management is most effective at reducing the high toll of this infection.

Initial research suggests a wide range of potential symptoms including those that would be expected with a respiratory virus (e.g., fever, cough) as well as gastrointestinal issues, dizziness, inability to concentrate, and effects on the sense of smell and taste. Additionally, there are a wide range of treatments, both prescribed and over-the-counter, that are being used to manage symptoms. Systematic data collection and analytics will contribute empirical information about benefits and risks that could have immediate public health impact. This registry will enroll participants in an observational, direct-to-participant longitudinal study to assess disease risk, progression, treatments, and vaccines.

Objectives: The objectives of this study are to:

1. Identify factors that may impact the occurrence, severity, or duration of COVID-19 infections including examining the role of underlying health conditions, prescription and over-the-counter medications, vitamins and supplements.
2. Assess post-vaccine symptoms and COVID-19 infection among participants reporting a COVID-19 vaccination

Study Design: This is an observational, direct-to-participant, web-based, longitudinal study of adults with COVID-19 or COVID-19 like illness to better understand risk factors, symptoms, and treatments for COVID-19 illness and vaccine safety and effectiveness. This study will be launched and conducted in the US and UK. Participants will be recruited through postings from partner organizations such as governments and professional associations as well as support from advertising, social media, and public relations. People with COVID-19, COVID-19 like symptoms, exposure to COVID-19, and/or COVID-19 vaccination will be asked to visit the online study portal. All study data will be reported by participants within the web-based study portal. Participants will complete an initial baseline survey reporting their demographics, relevant medical history, testing, vaccination, symptoms, use of prescription and non-prescription medications (prophylactic and curative) as well as use of supplements (e.g., vitamins, minerals, and herbals) and other factors. The study follow-up period is 12 months. During the first month of follow-up participants will be invited to complete a symptom diary weekly to gauge symptom progression and severity and to provide updates on pharmaceutical and non-pharmaceutical interventions as well as healthcare encounters. Reporting will then reduce to monthly for Month 2 through 12. Participants reporting COVID-19 vaccination (first or second dose) will be moved into weekly follow-up, if not already in weekly follow-up, for 4 weeks after vaccination to capture subsequent symptoms and healthcare encounters as well as a second vaccine dose if applicable. This survey schedule represents reminders for survey completion, noting the technology will allow for participants to enter data at any time during the follow-up window.

Study Population: The study population will include adults aged 18 and older who have COVID-19, have COVID-19 like symptoms, were exposed to COVID-19, or received a COVID-19 vaccine. Participants must have access to an internet-connected computer, smartphone or tablet to answer registry questions.

Data Management and Quality Assurance: Data will be collected using a web-based, mobile-friendly portal. Data will be collected and stored in a HIPAA-compliant manner consistent with high levels of privacy and security for storing sensitive information about participant health. Data will be encrypted during transit and at rest. Access privileges will be granular and tightly controlled with strong passwords required from administrative users. Personally identifiable information collected for registration, including personal contact information will be stored separately from other collected information and will only be accessible to staff with administrative privileges and with a specific and legitimate purpose to use that information.

Ethical and Regulatory Considerations: This observational study will be conducted in accordance with the protocol and all applicable laws and regulations including, but not limited to good pharmacoepidemiology practices (GPP), and the ethical principles that have their origins in the Declaration of Helsinki and applicable privacy laws. Data protection and privacy regulations will be strictly observed in capturing, forwarding, processing, and storing participant data. Every effort will be made to protect participant confidentiality according to the General Data Protection Regulation (GDPR) on the protection of individuals, and in compliance with EU-US Privacy Shield, and other relevant data privacy and protection regulations. An IRB/IEC must review and approve the protocol and informed consent form before any participants are enrolled. Before any protocol-directed data collection is performed, the participant must sign and date the IRB/IEC-approved informed consent form. This protocol will be posted on clinicaltrials.gov and the EU PAS Register (<http://www.encepp.eu/encepp/studiesDatabase.jsp>).

1. BACKGROUND AND RATIONALE

The ongoing coronavirus disease (COVID-19) pandemic has caused a worldwide crisis in terms of social, medical and financial systems. The number of cases globally has increased significantly since the first reported case in December 2019. Initially, the disease was thought to severely affect primarily older patients (60 years and above)¹ but as the virus continues to spread, it has become evident that several other patient populations are at high risk for hospitalization, complications, and even death².

The United States has been severely burdened by COVID-19, with over 28 million cases and 500,000 deaths reported as of 25 February 2021³. Additionally, there have been evolving reports of COVID-19 symptoms and progression^{4,5,6,7}, making it difficult for people to determine when they should seek medical attention and/or quarantine for suspected COVID-19 illness. Therefore, there is a need for systematic data collection from people who may be infected with COVID-19 but may not have access to a test to confirm their diagnosis.

Currently, there is a paucity of data describing disease risk, symptoms, and non-prescription medication use including supplements among the broader non-hospitalized community. Most publicly available data is limited to surveillance of the number of tested cases and the number of deaths, with little to no longitudinal follow-up of symptom progression, outcomes, treatments, and other related information. In addition, there is a need for long-term follow-up for people receiving COVID-19 vaccinations to continue to monitor safety and effectiveness outside of well controlled clinical trials and as COVID-19 strains evolve over time.

With recent Emergency Use Authorization of several COVID-19 vaccines, there is also a need to understand broad and long-term safety and effectiveness of the COVID-19 vaccines over time and as new strains emerge.

Systematic data collection and analytics would contribute empirical information about benefits and risks that could have immediate public health impact. This Registry will enroll participants in an observational, direct-to-participant longitudinal study to assess disease risk, progression, treatments, and vaccines.

2. OBJECTIVES

The objectives of this study are to:

1. Identify factors that may impact the occurrence or severity of COVID-19 infections including examining the role of underlying health conditions, prescription and over-the-counter medications, vitamins and supplements.
2. Assess post-vaccine symptoms and COVID-19 infection among participants reporting a COVID-19 vaccination

3. STUDY DESIGN

3.1 Study Description

This is an observational, direct-to-participant, web-based, longitudinal study of adults with potential exposure to COVID-19 to better understand risk factors, symptoms, and treatments for COVID-19 illness as well as vaccine safety and effectiveness. This study will be conducted in the US and UK. Participants will be recruited through postings from partner organizations such as governments and professional associations as well as support from advertising, social media, and public relations. People who have been vaccinated against COVID, who have COVID-like symptoms, or were exposed to COVID-19 will be asked to visit a portal landing page. All study data will be reported by participants within the web-based study portal. Upon consent and enrollment, participants will complete an initial baseline survey reporting their demographics, relevant medical history, symptoms, use of prescription and non-prescription medications (prophylactic and curative) as well as use of supplements (e.g., vitamins, minerals, herbals) and other factors. Participants are then followed for 12 months. During Month 1, participants will complete a symptom diary to record symptom progression and severity and provide updates on pharmaceutical and non-pharmaceutical interventions as well as healthcare encounters once a week. During Months 2 through 12, follow-up is reduced to twice a month to reduce patient burden and capture longer-term disease progression (now often referred to as “long COVID”) and treatment. Longer follow-up is required to assess symptoms that may linger or worsen.

No medical advice will be provided; links to credible medical resources about COVID-19 will be made available.

3.2 Study Population

There is no sample size restriction for this study. This study is designed for open enrollment of all eligible participants and can accommodate millions of respondents.

3.2.1 Inclusion Criteria

The following criteria must be met in order to be enrolled in the study:

- Adult (18 years or older)
- Currently living in the US or UK
- Have COVID-19 or COVID-19 like symptoms
- Received a COVID-19 vaccine
- Potential exposure to COVID-19

- Have regular access to a computer, smartphone or tablet and sufficient internet to support registry demands (note: this registry is designed to operate well even in regions with low bandwidth)
- Willing and able to provide informed consent
- Willing and able to follow the procedures of the study

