3.2.3 Study Enrollment

The registry will engage participants through postings from partner organizations such as governments and professional associations as well as support from advertising, social media, and public relations to visit a portal landing page. Once on the landing page, the participant will answer questions to confirm eligibility, consent into the study, and then register by providing an email address and, optionally, a mobile phone number. As part of consenting into this registry, participants also agree to be contacted for future research opportunities. Participants are not required to participate in any future studies, and there is no consequence for ignoring the request or declining to participate. Participation in any future research opportunities will require a separate, study-specific consent.

At enrollment, participants will also be asked to provide an alternative contact (next of kin or close friend) who may be contacted if we are unable to reach the participant. The intent here is to minimize loss to follow-up and to allow for proxy data collection in the event of serious illness or death.

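### The inclusion list in section 3.2.1 requires illness, vaccination and exposure together, while the synopsis and section 3.1 treat them as alternative routes of entry

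*Protocol*

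**What the plan says.** Protocol section 3.2.1 introduces its list with "The following criteria must be met in order to be enrolled in the study". The items are adult age, residence in the US or UK, having COVID-19 or similar symptoms, "Received a COVID-19 vaccine", potential exposure, device and internet access, consent, and willingness to follow procedures. No *or*, *any of* or *at least one of* appears between the items or above the three COVID-related ones.

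Three other statements treat those COVID-related items as alternatives:

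- Synopsis, Study Population: adults "who have COVID-19, have COVID-19 like symptoms, were exposed to COVID-19, or received a COVID-19 vaccine".
- Synopsis, Study Design: "People with COVID-19, COVID-19 like symptoms, exposure to COVID-19, and/or COVID-19 vaccination will be asked to visit the online study portal".
- Section 3.1, recruitment sentence: "People who have been vaccinated against COVID, who have COVID-like symptoms, or were exposed to COVID-19" are directed to the portal landing page.

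Section 3.2.3 gives the list its practical role: on the landing page "the participant will answer questions to confirm eligibility". Section 3.3.1, which covers baseline data for all enrolled participants, asks whether a vaccine was received and then puts further questions to the vaccinated only.

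**The concern.** Section 3.2.1 is the operative eligibility text. As worded, it makes vaccination, illness and exposure joint conditions, in the same list as conditions that plainly apply to everyone. The rest of the protocol describes a wider population.

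If the literal rule were applied, the consequences for the objectives in section 2 would be these:

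- **Objective 1 (occurrence and severity).** Every entrant would already have COVID-19 or similar symptoms, so nobody well at entry could be followed for occurrence. No unvaccinated person could enter at all.
- **Objective 2 (post-vaccine symptoms and infection among the vaccinated).** This could still be pursued, but only in vaccinees who also had illness or similar symptoms and potential exposure at entry. Vaccinees who enrol while well would be lost.

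Eligibility is confirmed by answers given on a portal. A programmer who turned the written list directly into screening logic would produce the narrow rule. An analyst describing the source population would find two definitions that disagree.

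**Working it through.** The plan gives no figure on this point, so the check is a logical comparison of the two rules.

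**Inputs**

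- A = has COVID-19 or similar symptoms (section 3.2.1).
- B = has received a COVID-19 vaccine (section 3.2.1).
- C = potential exposure (section 3.2.1), taken for now as the same condition as exposure in the synopsis and section 3.1.
- Rule 1, section 3.2.1 as written: A and B and C.
- Rule 2, synopsis Study Population and both recruitment sentences: A or B or C.

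The universal requirements (age, residence, access, consent, willingness) are taken as met. Three yes/no conditions give 2 × 2 × 2 = 8 profiles.

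| Profile | A | B | C | Rule 1 | Rule 2 |
|---|---|---|---|---|---|
| 1 | yes | yes | yes | eligible | eligible |
| 2 | yes | yes | no | refused | eligible |
| 3 | yes | no | yes | refused | eligible |
| 4 | yes | no | no | refused | eligible |
| 5 | no | yes | yes | refused | eligible |
| 6 | no | yes | no | refused | eligible |
| 7 | no | no | yes | refused | eligible |
| 8 | no | no | no | refused | refused |

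**Results**

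- Rule 1 admits 1 of 8 and Rule 2 admits 7 of 8. They disagree on 7 − 1 = 6 profiles.
- Unvaccinated (profiles 3, 4, 7, 8): 0 of 4 under Rule 1, 3 of 4 under Rule 2.
- Vaccinated without COVID-19 or similar symptoms (profiles 5, 6): 0 of 2 under Rule 1, 2 of 2 under Rule 2.
- The remaining disagreement is profile 2, the ill vaccinee without potential exposure. The total is 3 + 2 + 1 = 6.

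**Sensitivity to the exposure wording.** Section 3.2.1 says *potential* exposure, whereas the synopsis population statement and the section 3.1 recruitment sentence speak of having been exposed. Suppose potential exposure were taken as true of everyone. Only the four profiles with C = yes (1, 3, 5, 7) then remain: Rule 1 admits 1 of 4 and Rule 2 admits 4 of 4. The conflict persists, and the *or* rule would then exclude nobody on these conditions. The exposure wording therefore has to be settled together with the joining word.

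**Which rule fits the rest of the protocol.** Under Rule 1 every entrant is vaccinated, so asking about vaccine receipt at baseline and branching on the answer (section 3.3.1) would be pointless. Under Rule 2 the branch is needed. Section 3.2.2 also spells out that meeting any one exclusion is enough to be ineligible. Section 3.2.1 has no corresponding statement for the three routes.

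**The case against.** The strongest reply is that the intent is not in doubt. The synopsis population statement uses *or*, both recruitment sentences agree, and the version history describes V4.0 as widening entry to vaccinated adults. On that view this is a missing connective that nobody would read literally. The point about intent stands, and it limits the claim to a contradiction in wording. It does not remove the need for correction, because section 3.2.1 governs eligibility and is applied by self-screening.

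A second reply is that the PDF conversion flattened a nested list. The three routes are consecutive, and nested bullets are flattened elsewhere, so they may well be grouped in the source. But lost indentation would not remove joining words, and the extracted text has no parent line stating a rule. The source layout cannot be confirmed from the text available.

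Several stronger readings are tempting but not supported:

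- **That enrolment was in fact restricted.** The portal questions are not shown, and nothing in the protocol demonstrates this.
- **That a planned comparison of vaccinated with unvaccinated people is lost.** Section 3.1 names vaccine effectiveness as a general aim, but no section specifies that comparison. Objective 2 is confined to vaccinated participants, and section 4.2.1 leaves in-depth analyses to supplementary plans.
- **That only symptomatic people would qualify.** A person with COVID-19 but no symptoms meets the illness item.
- **That the Table 1 footnote on first doses during follow-up proves unvaccinated entry under the current criteria.** People enrolled under earlier versions could also report a first dose, and the footnote covers second doses too.
- **That the opening design sentences are further conflicting eligibility rules.** They read "longitudinal study of adults with COVID-19 or COVID-19 like illness" (synopsis) and "longitudinal study of adults with potential exposure to COVID-19" (section 3.1). They are descriptive summaries, and the recruitment sentence in each place gives the wider population.

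**Conclusion.** The contradiction is real and lies in the governing section. As written, section 3.2.1 admits 1 of 8 illness, vaccination and exposure profiles, against 7 of 8 under the rule stated in the synopsis and implied by section 3.1. It refuses every unvaccinated person and every vaccinee without COVID-19 or similar symptoms. This conflicts with studying occurrence under Objective 1 and narrows Objective 2 without defeating it.

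The conclusion rests on two assumptions: that the extracted text has lost no joining words, and that exposure means the same thing in each place. The contradiction survives the alternative reading in which everyone counts as potentially exposed. The profile counts are logical combinations, not proportions of people; the number of people affected cannot be computed from the protocol. The literal rule would bear only on entry under the current criteria, since the registry was already open under earlier versions.

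This should be fixed, as a wording error in the eligibility rule. A reader might infer a flaw in the design or harm to enrolment, but the protocol shows neither.

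**What to change.** - In section 3.2.1, group the three routes under *at least one of the following*: (a) COVID-19 or similar symptoms; (b) exposure to COVID-19; (c) receipt of a COVID-19 vaccine.
- Keep age, residence, device and internet access, consent and willingness to follow procedures as requirements for everyone.
- Choose one exposure wording, potential or actual, and use it in section 3.2.1, the synopsis population statement and section 3.1.
- Confirm that the portal screening questions apply the same rule.

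The cost is one phrase in section 3.2.1, matching wording in two other places, and a check of the screening logic. Design, data collection and objectives stay as they are.

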3.2.2 Exclusion Criteria

Participants meeting ANY of the following criteria are not eligible for participation:

- Unable to provide informed consent
- Unable to perform the requested study tasks

3.2.3 Study Enrollment

The registry will engage participants through postings from partner organizations such as governments and professional associations as well as support from advertising, social media, and public relations to visit a portal landing page. Once on the landing page, the participant will answer questions to confirm eligibility, consent into the study, and then register by providing an email address and, optionally, a mobile phone number. As part of consenting into this registry, participants also agree to be contacted for future research opportunities. Participants are not required to participate in any future studies, and there is no consequence for ignoring the request or declining to participate. Participation in any future research opportunities will require a separate, study-specific consent.

At enrollment, participants will also be asked to provide an alternative contact (next of kin or close friend) who may be contacted if we are unable to reach the participant. The intent here is to minimize loss to follow-up and to allow for proxy data collection in the event of serious illness or death.

3.2.4 Participant Withdrawal

Participants may withdraw consent and discontinue participation in the study at any time. All survey data would be deleted from the central system and would not be included in any future data distributions. However, the data will not be withdrawn from past data distributions to partners or deleted from archival backup files.

3.3 Data Sources and Collection

This is a direct-to-participant registry. All data will be reported by participants through a web-enabled application. No visits or examinations, laboratory tests or procedures are mandated or required for this study. Table 1 outlines reminders for participants to complete surveys, noting the technology will allow for participants to enter data at any time during the follow-up window.

Table 1. Data Collection Schedule

	Enrollment /Baseline	Month 1 (once a week)	Month 2 through 12 (twice a month)
Informed Consent	X		
Demography	X		
Static Medical History and Risk Factors (e.g., height, weight, occupation)	X		
Medical History (e.g., diagnoses, concomitant medications, vitamins/supplements, pregnancy, seasonal flu vaccine)*	X	X*	X*
COVID-19 test, if conducted	X	X	X
COVID-19 vaccination including manufacturer, date, lot number and first shot or booster, post-vaccine symptoms, and healthcare encounters for possible reactions, if available	X	X**	X**
COVID-19 symptoms	X	X	X
COVID-19 medications, both prescription and OTC, that may be intended as prophylactic or curative treatments	X	X	X

*Participants will be asked during follow-up if they had any changes in their underlying medical history (e.g., new diagnoses, new medications). If yes, they will report changes in key medical history that may influence COVID-19 risk factors and/or recovery (e.g., new comorbidities, pregnancy, etc).

**Participants reporting COVID-19 vaccination (first or second dose) will be moved into weekly follow-up, if not already in weekly follow-up, for 4 weeks after vaccination to capture subsequent symptoms and healthcare encounters as well as a second vaccine dose if applicable.

